# 1. BACKGROUND AND DESIGN

The trial hypothesis under investigation is that treatment with aspirin is safe and improves important surrogate clinical outcomes in adult patients with ARDS.

The objective of the trial is

1. To conduct a prospective randomised, double-blind, allocation concealed, placebo-controlled phase 2 trial of aspirin as a treatment for ARDS.
2. To study the biological effects of aspirin on pulmonary and systemic
  - a. inflammatory responses,
  - b. epithelial and endothelial function and injury and
  - c. lipid inflammatory mediators

Subjects will be randomised to receive aspirin 75mg capsule or a placebo capsule enterally for up to 14 days. Subjects will be randomised in a 1:1 ratio using blocks of variable size. The first dose of the study drug will ideally be administered within 4 hours of randomisation and subsequent doses will be as close to 10 am as possible starting on the following calendar day.

Patients will be eligible to participate in the study if they fulfil the following criteria:

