## 6. ANALYSIS PRINCIPLES

Primary outcome measure is the OI at day 7. Unadjusted (primary analysis) and adjusted analysis will be carried out to test whether there is a statistically significant difference between the aspirin & placebo groups. Secondary analysis will be carried out, if the day 7 OI values are missing, using last value carry forward method.

Secondary outcome measures are OI, CRs, PF ratio, and SOFA score at day 4, 7, 14 and safety. Unadjusted and adjusted analysis will be carried out on OI, CRs, PF ratio, SOFA score, to test whether there is a statistically significant difference between the groups.

Unadjusted analysis will be carried out using Independent sample t-test. Adjusted analysis will be carried out using ANCOVA or [mixed modelling technique](#), based the number of data points available at each time point. Estimates & 95% confidence interval will be reported.

The number of AE, ARs, SAE, SARs, SUSARs and number (%) of patient experiencing the events will be reported. Fisher's exact test and proportion test will be used to check whether incidences of adverse events differ between the groups. Relative risk and 95% CI will be reported.

Exploratory analysis on mediators will be carried out using student t-tests or non-parametric alternative and Fishers Exact Test, presented by day where applicable. The estimates & 95% CIs will be reported. Statistical diagnostic methods will be used to check for violations of the assumptions, and transformations will be performed if required. For binary outcome measures, risk ratios and associated 95% CI will be calculated. Survival analysis technique will be used for time-to-event data. Median survival time & 95% CI will be estimated using Kaplan-Meier estimation method and the Kaplan-Meier plots will be presented. In all time-to-event analyses, patients that did not experience the event in question (e.g. death) were censored on the date last seen or 90 days. The equality of survivorship function of aspirin & placebo group will be tested

for significance using a log-rank  $\chi^2$  test. Hazard ratios (HRs) & 95% CIs will be reported if the proportionality assumption holds.

Correlations between changes in the biological markers measured and physiological and clinical outcomes will be assessed by appropriate graphical and statistical methods including Pearson's (or Spearman's) correlation coefficient.

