A secondary analysis excluding patients identified to have aspirin resistance will also be undertaken.

Analyses will be conducted according to intention to treat principle. All statistical tests will be 2-sided and a p-value of 0.05 will be considered as statistically significant, unless adjustment for multiple testing was needed. A single analysis is planned at the end of the trial. Every effort will be made to minimise missing baseline and outcome data in this trial. Any ad-hoc analysis will be reported as per the regulatory requirement.

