**Table A2. Treatment after Trial Entry**

	Aspirin N = <n>	Placebo N = <n>
Number of patients who received at least one dose of treatment	n	n
Duration of study drug (days)	xx.x ± x.x	xx.x ± x.x
Time from randomisation to start of study drug (hours)	xx.x (xx.x to xx.x)	xx.x (xx.x to xx.x)
Reasons for termination of study drug		
14 days after randomisation	n	n
Study drug related adverse event	n	n
Discharge from critical care	n	n
Death	n	n
Discontinuation of active medical treatment	n	n
Request for discontinuation of trial drug by patient or legal representative	n	n
Decision by a physician on safety grounds	n	n
Clinical indication for treatment with Aspirin	n	n
Other	n	n
Protocol deviations/ violations		
Eligibility	n (xx.x%)	n (xx.x%)
Study Drug Administration		
Did not receive allocated treatment a	n (xx.x%)	n (xx.x%)
Received treatment of other group b	n (xx.x%)	n (xx.x%)
Study drug omitted in error c	n (xx.x%)	n (xx.x%)
Study drug given in error	n (xx.x%)	n (xx.x%)
Other	n (xx.x%)	n (xx.x%)

Mean ± SD or Median (p25 to p75) presented for continuous variables and no. or no. (%) for all categorical variables a- Numbers based on study drug administration data, b- Numbers based on the randomisation listing held by trial Statistician, c- Numbers based on Protocol deviation data

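### No safety population is defined and intention to treat is unqualified, so the only planned adverse-event comparison is by allocated arm, which would mute any harm of aspirin if patients go undosed or get the other arm's drug

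*SAP*

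**What the plan says.** Section 6 closes with a general rule: "Analyses will be conducted according to intention to treat principle". The same section makes safety a formal outcome ("Secondary outcome measures are OI, CRs, PF ratio, and SOFA score at day 4, 7, 14 and safety") and fixes how it is tested: "Fisher's exact test and proportion test will be used to check whether incidences of adverse events differ between the groups", with relative risks and 95% confidence intervals. Section 7.5 reports events by arm, and the adverse-event table in Appendix 1 has Aspirin and Placebo columns with a patient number for each. No safety, as-treated or at-least-one-dose set is defined anywhere in the SAP.

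Table A2 provides for departures from allocated treatment. It has rows for "Number of patients who received at least one dose of treatment", for patients who did not get their allocated treatment, for "Received treatment of other group", and for stopping study drug because of "Clinical indication for treatment with Aspirin". Its footnotes name the administration records and the randomisation listing as sources.

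The hypothesis in Section 1 is that "treatment with aspirin is safe and improves important surrogate clinical outcomes". Dosing lasts up to 14 days, and Table 1 shows adverse events also being collected in the Day 15-42 column.

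**The concern.** Grouping by allocation is usually the cautious choice for efficacy, because non-adherence shrinks a benefit. For harm it works the other way. If aspirin raises the risk of an event, an aspirin-arm patient who never took a capsule adds to the aspirin denominator at unexposed risk. A placebo-arm patient given aspirin capsules adds events to the placebo column. Both reduce the contrast, and a reduced contrast favours the hypothesis of safety. With about 30 patients per arm, a few such patients can change the estimate. The SAP plans to count them in Table A2 but does not carry the counts into the safety comparison.

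**Working it through.** **The plan's own figures.** The SAP gives no event rate, departure rate or power for safety. Its only sample-size figure is for the oxygenation index. A difference of 39 with SD 51, two-sided 0.05 and 80% power gives 27.84 by the t-test, so 28 per arm (power 80.2%). With 5% dropout, 28/0.95 = 29.5, so 30 per arm. The SAP's 56 and 60 are reproduced. This point does not affect them; they only supply the denominator of 30.

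**Formula.** Let p1 be the event risk with aspirin and p0 the risk without. Let d be the fraction of the aspirin arm not exposed to aspirin, and e the fraction of the placebo arm exposed to it.

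- Aspirin-arm risk = (1 − d)·p1 + d·p0
- Placebo-arm risk = (1 − e)·p0 + e·p1
- Relative risk (RR) = ratio of the two

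**Assumed risks p1 = 20%, p0 = 5%** (not from the SAP):

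| Assumed departures | Aspirin arm | Placebo arm | RR |
|---|---|---|---|
| None | 20% | 5% | 4.0 |
| 1 of 30 aspirin patients undosed | (29×20 + 1×5)/30 = 19.5% | 5% | 3.9 |
| 1 of 30 in each arm | 19.5% | (29×5 + 1×20)/30 = 5.5% | 3.55 |
| 3 of 30 in each arm | 0.9×20 + 0.1×5 = 18.5% | 0.9×5 + 0.1×20 = 6.5% | 2.85 |

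In the last row the risk difference falls from 15 to 12 points. The third row needs only one patient per arm given the other arm's drug.

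**Second set of assumed risks, 30% v 10%, 30 per arm, with exact power of the two-sided Fisher test:**

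- No departures: RR 3.00, power 37%.
- One undosed aspirin patient: RR 2.93, power 35%.
- One undosed aspirin patient, one wrong-drug patient per arm, and one further placebo patient exposed to aspirin: aspirin arm (28×30 + 2×10)/30 = 28.7%, placebo arm (28×10 + 2×30)/30 = 11.3%, RR 2.53, power 27%.
- Three undosed, one wrong-drug per arm, three further placebo patients exposed: aspirin arm (26×30 + 4×10)/30 = 27.3%, placebo arm (26×10 + 4×30)/30 = 12.7%, RR 2.16, power 19%.

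**Which departures dilute.** An undosed placebo patient keeps risk p0, so the placebo arm and the RR do not change. An aspirin-arm patient who stops study drug and then takes clinical aspirin keeps risk p1, so the aspirin arm does not change. Only undosed aspirin-arm patients and patients exposed to the opposite treatment reduce the contrast.

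**The case against.** The general rule does not name safety, and the adverse-event table leaves its patient numbers blank without saying who is counted. A reader might infer that the sponsor deliberately chose an allocated-arm safety comparison. The documents do not show that. What stands is that the rule is unqualified, sits in the section that specifies the adverse-event tests, and has no alternative population beside it. Followed as written, it gives allocated arms.

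A reader might also infer that every dosing departure dilutes harm. That is not so, as shown in the working. Departures in intensive care may also track severity: an undosed aspirin-arm patient who dies adds an event to that arm and can move the relative risk away from 1.

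A third inference is that the fall from 4.0 to 2.8 is to be expected. It rests on assumed risks and on 10% misexposure in each arm at once. The Section 1 exclusions remove recent aspirin users, patients with a proven indication for aspirin and patients who cannot take enteral drugs, so departures may be few. The calculation also gives each misexposed patient the full aspirin risk, even after a single capsule, and models an aspirin-related event, whereas the adverse-event rows count events of any cause.

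Finally, Table A2 lists a clinical indication only as a reason for stopping study drug. That placebo patients then take aspirin is a reasonable inference but is not stated.

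Table A2 would let a reader see the departures beside the safety results, adverse reactions have their own rows, and the monitoring committee reviews safety by group. These help interpretation but do not supply a comparison by drug received. Power to detect harm is low even with perfect adherence (37% in the second set of assumptions), so sample size is the larger limit. That does not justify losing more power to an avoidable choice.

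**Conclusion.** The point holds as a gap in how the safety comparison is specified. It is not a demonstrated bias. The SAP's only stated rule leads to adverse events being compared by allocated arm alone, although it plans to record who was dosed and with what. If aspirin causes harm, undosed aspirin-arm patients and patients given the other arm's drug would pull the relative risk towards 1, in favour of the stated hypothesis. Under assumed risks of 20% v 5%, the effect runs from negligible (4.0 to 3.9) through about 3.5 to about 2.8, depending on assumed counts of one undosed patient, 1 of 30 in each arm, or 3 of 30 in each arm. The SAP cannot say which applies. The conclusion assumes that the general rule covers safety, that aspirin raises the event risk, and that departures are unrelated to a patient's underlying risk.

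**What to change.** In Section 6:

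- Limit intention to treat to the efficacy analyses.
- Base the main adverse-event table on patients who received at least one dose of study drug, grouped by the study drug received. Use the administration records and randomisation listing already cited under Table A2.
- State in advance how patients who received both drugs are assigned, for example that any aspirin capsule places the patient in the aspirin group.
- List separately any event after a recorded start of non-trial aspirin, including those in the Day 15-42 window. Grouping by study drug received does not settle where these belong.
- Keep the allocated-arm table as supportive.

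The cost is a short change to the text, one extra table and one listing, from data already collected. The change should be made before unblinding, so that the choice of population cannot be seen as driven by results. The drawback is that groups formed by drug received are no longer strictly the randomised ones. The supportive table covers that.

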## **7. ANALYSIS DETAILS**

The results of the analyses will be reported following the principle of the ICH E3 guidelines on the Structure and Content of Clinical Study Reports and CONSORT reporting guidelines.

### **7.1 Recruitment and follow-up patterns**

- The number of withdrawals by treatment group

### **7.2 Baseline Characteristics**

The randomisation is stratified by vasopressor requirement. Refer to table A1. Baseline characteristics at trial entry

### **7.3 Trial treatment**

Refer to table A2. Treatment after trial entry

## 7.4 Main Clinical Endpoints

- Oxygenation Index (OI) at day 7 or the last available OI prior to patient discontinuation from the study, Mean  $\pm$  SD by treatment arm
- Oxygenation index (OI) at days 4 and 14, Mean  $\pm$  SD by treatment arm
- Respiratory compliance (CRs) at days 4, 7 and 14, Mean  $\pm$  SD by treatment arm
- P/F ratio at days 4, 7 and 14, Mean  $\pm$  SD by treatment arm
- Sequential organ failure assessment (SOFA) score from baseline to day 4, 7, and 14, Mean  $\pm$  SD by treatment arm

Refer to table A 1. Main Clinical Outcome Variables: PF Ratio, Oxygenation Index, SOFA, Respiratory Compliance at each visit

## 7.5 Toxicity/ Symptoms

- Adverse Events (AEs), Serious adverse events (SAEs), Suspected unexpected serious adverse reactions (SUSARs), and Death, no. (%) by treatment arm

Refer to table A7. Adverse events/reactions (AE/AR), serious adverse events/reactions (SAE/SAR) & suspected unexpected serious adverse reactions

# 8. ADDITIONAL INFORMATION

## 8.1 Trial management group (TMG)

The CI will take responsibility for the need to change the protocol for any reason, reviewing relevant information from other sources and considering recommendations from the DMEC. Day to day management will be undertaken via a trial management group composed of the CI and supporting staff. They will meet on a monthly basis to discuss study issues. The NICTU will be the Trial Co-ordinating Centre. Statistician's report on the accrual rate will be held in the Statistics section of the trial master file.

## 8.2 Data Monitoring and Ethics Committee (DMEC)

A DMEC will be appointed. The committee will be independent of the study team and will comprise Dr [name], an intensive care clinician, Prof. [name] a clinician with experience in undertaking clinical trials with aspirin, as well as Prof. [name] Director of the

All Ireland Hub for Trials Methodology, an experienced clinical trialist. The DMEC will meet to agree conduct and remit. The sponsor has recommended the DMEC meet once patient recruitment reaches 5, 20, 40 & 60. Accumulating information relating to recruitment, data quality will be presented at the open session of the DMEC. Toxicity details based on pooled data and total numbers of events for the primary outcome measure and other outcome measures may be presented to open session, at the discretion of the DMC. In addition to all the material available in the open session, the closed session material will include safety data by treatment group. It may include efficacy data by treatment group, depending on the planned interim analysis. Data reported by treatment group should be blinded where possible, unless the DMC requests otherwise. In the event of an occurrence of an unexpected severe adverse reaction an additional unplanned DMEC meeting will be convened. As this is a phase 2 trial, an interim analysis of efficacy is not planned although this issue can be discussed by the DMEC as required. The DMEC will function primarily as a check for safety, reviewing adverse events. They will report any issues pertaining to safety to the Chief Investigator. It will be the responsibility of the Chief Investigator to inform the sponsor who will take appropriate action to halt the trial if concerns exist about patient safety. Statisticians (Closed and open) reports will be held in the Statistics section of the trial master file.

# APPENDIX 1. EXAMPLE DRAFT SUMMARY TABLES

**Table A1. Baseline characteristics at trial entry**

Variable	A	B	Total
	N = <n>	N = <n>	N = <n>
Age (years)	xx.x ± x.x	xx.x ± x.x	xx.x ± x.x
Gender			
Male	n (xx.x%)	n (xx.x%)	n (xx.x%)
Female	n (xx.x%)	n (xx.x%)	n (xx.x%)
Height (cm)	xx.x ± x.x	xx.x ± x.x	xx.x ± x.x
Weight (kg)	xx.x ± x.x	xx.x ± x.x	xx.x ± x.x
Vasopressor Requirement			
No	n (xx.x%)	n (xx.x%)	n (xx.x%)
Yes	n (xx.x%)	n (xx.x%)	n (xx.x%)
Worst PaO 2 :FiO 2 ratio (kPa) (pre-randomisation)	xx.x ± x.x	xx.x ± x.x	xx.x ± x.x
PaO 2 :FiO 2 ratio (kPa) +	xx.x ± x.x	xx.x ± x.x	xx.x ± x.x
Plateau Pressure (cmH 2 O) +	xx.x ± x.x	xx.x ± x.x	xx.x ± x.x
Lowest Platelets (x10  /L) +	xx.x ± x.x	xx.x ± x.x	xx.x ± x.x
Tidal Volume (ml/kg PBW) +			
All patients	xx.x ± x.x	xx.x ± x.x	xx.x ± x.x
Controlled ventilation	xx.x ± x.x	xx.x ± x.x	xx.x ± x.x
Tidal Volume (ml/kg PBW) Day 1			
All patients	xx.x ± x.x	xx.x ± x.x	xx.x ± x.x
Controlled ventilation	xx.x ± x.x	xx.x ± x.x	xx.x ± x.x
Aetiology of ARDS*			
Smoke/toxin inhalation	n (xx.x%)	n (xx.x%)	n (xx.x%)
Gastric content aspiration	n (xx.x%)	n (xx.x%)	n (xx.x%)
Near drowning	n (xx.x%)	n (xx.x%)	n (xx.x%)
Thoracic trauma	n (xx.x%)	n (xx.x%)	n (xx.x%)
Pneumonia	n (xx.x%)	n (xx.x%)	n (xx.x%)
Sepsis	n (xx.x%)	n (xx.x%)	n (xx.x%)
Cardiopulmonary bypass	n (xx.x%)	n (xx.x%)	n (xx.x%)
Pancreatitis	n (xx.x%)	n (xx.x%)	n (xx.x%)
Non-thoracic trauma	n (xx.x%)	n (xx.x%)	n (xx.x%)
Other	n (xx.x%)	n (xx.x%)	n (xx.x%)
Mode of Ventilation +			
Controlled ventilation	n (xx.x%)	n (xx.x%)	n (xx.x%)
PS	n (xx.x%)	n (xx.x%)	n (xx.x%)
Other	n (xx.x%)	n (xx.x%)	n (xx.x%)
SAPs score (predicted mortality %)	xx.x ± x.x	xx.x ± x.x	xx.x ± x.x
APACHE II Score	xx.x ± x.x	xx.x ± x.x	xx.x ± x.x

Variable	A	B	Total
	N = <n>	N = <n>	N = <n>
Murray Lung Injury Score (LIS)	xx.x ± x.x	xx.x ± x.x	xx.x ± x.x
Total SOFA Score +	xx.x ± x.x	xx.x ± x.x	xx.x ± x.x
Oxygenation Index (cmH 2 O/kPa) +	xx.x ± x.x	xx.x ± x.x	xx.x ± x.x
Lowest Mean Arterial Pressure (mmHg) +	xx.x ± x.x	xx.x ± x.x	xx.x ± x.x

Mean ± SD presented for continuous variables and no. (%) for categorical variables.

+ At randomisation

\* <##> patient had more than one cause

**Table A2. Treatment after Trial Entry**

	Aspirin N = <n>	Placebo N = <n>
Number of patients who received at least one dose of treatment	n	n
Duration of study drug (days)	xx.x ± x.x	xx.x ± x.x
Time from randomisation to start of study drug (hours)	xx.x (xx.x to xx.x)	xx.x (xx.x to xx.x)
Reasons for termination of study drug		
14 days after randomisation	n	n
Study drug related adverse event	n	n
Discharge from critical care	n	n
Death	n	n
Discontinuation of active medical treatment	n	n
Request for discontinuation of trial drug by patient or legal representative	n	n
Decision by a physician on safety grounds	n	n
Clinical indication for treatment with Aspirin	n	n
Other	n	n
Protocol deviations/ violations		
Eligibility	n (xx.x%)	n (xx.x%)
Study Drug Administration		
Did not receive allocated treatment a	n (xx.x%)	n (xx.x%)
Received treatment of other group b	n (xx.x%)	n (xx.x%)
Study drug omitted in error c	n (xx.x%)	n (xx.x%)
Study drug given in error	n (xx.x%)	n (xx.x%)
Other	n (xx.x%)	n (xx.x%)

Mean ± SD or Median (p25 to p75) presented for continuous variables and no. or no. (%) for all categorical variables a- Numbers based on study drug administration data, b- Numbers based on the randomisation listing held by trial Statistician, c- Numbers based on Protocol deviation data

**Table A3. Main Clinical Outcome Variables: PF Ratio, Oxygenation Index, SOFA, Respiratory Compliance at each visit**

	Unadjusted, Mean $\pm$ SD			Mean Difference (95% CI)	p-value	Adjusted, Mean $\pm$ SE		Mean Difference (95% CI)	p-value
	All patients	Aspirin	Placebo			Aspirin	Placebo		
Primary outcome; OI at day 7									
Observed values (n=<n>)	xx.x $\pm$ x.x	xx.x $\pm$ x.x	xx.x $\pm$ x.x	xx.x (xx.x to xx.x)	0.xxx	xx.x $\pm$ x.x	xx.x $\pm$ x.x	xx.x (xx.x to xx.x)	0.xxx
Imputed values(n=<n>)*	xx.x $\pm$ x.x	xx.x $\pm$ x.x	xx.x $\pm$ x.x	xx.x (xx.x to xx.x)	0.xxx	xx.x $\pm$ x.x	xx.x $\pm$ x.x	xx.x (xx.x to xx.x)	0.xxx
Oxygenation Index									
Baseline (n=<n>)	xx.x $\pm$ x.x	xx.x $\pm$ x.x	xx.x $\pm$ x.x	xx.x (xx.x to xx.x)	0.xxx				
Day 4 (n=<n>)	xx.x $\pm$ x.x	xx.x $\pm$ x.x	xx.x $\pm$ x.x	xx.x (xx.x to xx.x)	0.xxx	xx.x $\pm$ x.x	xx.x $\pm$ x.x	xx.x (xx.x to xx.x)	0.xxx
Day 14 (n=<n>)	xx.x $\pm$ x.x	xx.x $\pm$ x.x	xx.x $\pm$ x.x	xx.x (xx.x to xx.x)	0.xxx	xx.x $\pm$ x.x	xx.x $\pm$ x.x	xx.x (xx.x to xx.x)	0.xxx
Respiratory compliance									
Baseline (n=<n>)	xx.x $\pm$ x.x	xx.x $\pm$ x.x	xx.x $\pm$ x.x	xx.x (xx.x to xx.x)	0.xxx				
Day 4 (n=<n>)	xx.x $\pm$ x.x	xx.x $\pm$ x.x	xx.x $\pm$ x.x	xx.x (xx.x to xx.x)	0.xxx	xx.x $\pm$ x.x	xx.x $\pm$ x.x	xx.x (xx.x to xx.x)	0.xxx
Day 7 (n=<n>)	xx.x $\pm$ x.x	xx.x $\pm$ x.x	xx.x $\pm$ x.x	xx.x (xx.x to xx.x)	0.xxx	xx.x $\pm$ x.x	xx.x $\pm$ x.x	xx.x (xx.x to xx.x)	0.xxx
Day 14 (n=<n>)	xx.x $\pm$ x.x	xx.x $\pm$ x.x	xx.x $\pm$ x.x	xx.x (xx.x to xx.x)	0.xxx	xx.x $\pm$ x.x	xx.x $\pm$ x.x	xx.x (xx.x to xx.x)	0.xxx
PF ratio									
Baseline (n=<n>)	xx.x $\pm$ x.x	xx.x $\pm$ x.x	xx.x $\pm$ x.x	xx.x (xx.x to xx.x)	0.xxx				
Day 4 (n=<n>)	xx.x $\pm$ x.x	xx.x $\pm$ x.x	xx.x $\pm$ x.x	xx.x (xx.x to xx.x)	0.xxx	xx.x $\pm$ x.x	xx.x $\pm$ x.x	xx.x (xx.x to xx.x)	0.xxx
Day 7 (n=<n>)	xx.x $\pm$ x.x	xx.x $\pm$ x.x	xx.x $\pm$ x.x	xx.x (xx.x to xx.x)	0.xxx	xx.x $\pm$ x.x	xx.x $\pm$ x.x	xx.x (xx.x to xx.x)	0.xxx
Day 14 (n=<n>)	xx.x $\pm$ x.x	xx.x $\pm$ x.x	xx.x $\pm$ x.x	xx.x (xx.x to xx.x)	0.xxx	xx.x $\pm$ x.x	xx.x $\pm$ x.x	xx.x (xx.x to xx.x)	0.xxx
SOFA									
Baseline (n=<n>)	xx.x $\pm$ x.x	xx.x $\pm$ x.x	xx.x $\pm$ x.x	xx.x (xx.x to xx.x)	0.xxx				
Day 4 (n=<n>)	xx.x $\pm$ x.x	xx.x $\pm$ x.x	xx.x $\pm$ x.x	xx.x (xx.x to xx.x)	0.xxx	xx.x $\pm$ x.x	xx.x $\pm$ x.x	xx.x (xx.x to xx.x)	0.xxx
Day 7 (n=<n>)	xx.x $\pm$ x.x	xx.x $\pm$ x.x	xx.x $\pm$ x.x	xx.x (xx.x to xx.x)	0.xxx	xx.x $\pm$ x.x	xx.x $\pm$ x.x	xx.x (xx.x to xx.x)	0.xxx
Day 14 (n=<n>)	xx.x $\pm$ x.x	xx.x $\pm$ x.x	xx.x $\pm$ x.x	xx.x (xx.x to xx.x)	0.xxx	xx.x $\pm$ x.x	xx.x $\pm$ x.x	xx.x (xx.x to xx.x)	0.xxx

\* Last value carried forward

**Table A4. Mixed model Estimates (Clinical outcomes, Haemodynamic & Oxygenation parameters and laboratory variables)**

Variable	Estimate (95% CI)	df	P>chi2
Group	x.xx (x.xx to x.xx)	n	0.xxx
Day	x.xx (x.xx to x.xx)	n	0.xxx
Group*Day	x.xx (x.xx to x.xx)	n	0.xxx

